### 9.1.1 Sensitivity Analysis

The analyses described in [Section 9.1](#) will be applied to the 3 assessments defined in “[Section 6.3.1 Response in Investigator’s Global Assessment](#) , 2) Sensitivity Analysis.”

## 9.2 Secondary Endpoints

### 9.2.1 Incidence of Success in IGA at Week 1 and Week 8

Incidence of success in IGA at Week 1 and Week 8 (as well as Week 2 and Week 6) will be analyzed in the same manner as described in [Section 9.1](#).

The change in incidence of success in IGA (the incidence of success in IGA in the primary analysis and the incidence of success in IGA defining responders as subjects with an improvement in IGA to 0 [clear] or 1 [almost clear]) will be plotted by timepoint for each treatment group.

### **9.2.2 Change From Baseline in IGA at Week 1, Week 4, and Week 8**

Based on the OC data set, the change from baseline in IGA (at Week 1, Week 2, Week 4, Week 6, and Week 8; if the timing of discontinuation falls within the allowable window of a timepoint, the data at discontinuation will be included as the data for the timepoint) will be analyzed using the mixed-model repeated measures (MMRM) analysis with treatment (0.3% or 1% OPA-15406 groups, and vehicle group), timepoint, and interaction between treatment and timepoint as factors and baseline IGA as a covariate.

An unstructured covariance matrix will be used to model the within-subject errors and Kenward-Roger method will be used to calculate the standard error of fixed-effects and the degree of freedom. If the MMRM procedure fails to converge under unstructured covariance structure, the following structure will be used in the order of 1) heterogeneous toeplitz, 2) heterogeneous autoregressive of order 1, 3) heterogeneous compound symmetry, and the first (co)variance structure converging to the best fit will be used.

The least square mean of each treatment group will be calculated by timepoint. The difference in the least square mean between the vehicle group and each OPA-15406 group, and the two-sided 95% confidence interval and p-value will also be calculated at Week 1, Week 4, and Week 8 (as well as at Week 2 and Week 6). The least square mean and the standard error will be plotted by timepoint for each treatment group.

The SAS code to conduct the MMRM analysis is shown below.

```
proc mixed method = reml ;  
  class Treatment Visit Subject ;  
  model Change = Treatment Visit Treatment*Visit Baseline/s ddfm = kr ;  
  repeated Visit/type = un sub = Subject ;  
  lsmeans Treatment*Visit/pdiff cl alpha = 0.05 ;  
  run;
```

“Baseline” represents the IGA at baseline.

The SAS code to use when the MMRM procedure fails to converge under the unstructured covariance structure is shown below. (Designate *type* = *TOEPh* for heterogeneous toeplitz, *type* = *ARH*(1) for heterogeneous autoregressive of order 1, and *type* = *CSH* for heterogeneous compound symmetry).

```
proc mixed method = reml empirical ;  
  class Treatment Visit Subject ;  
  model Change = Treatment Visit Treatment*Visit Baseline/s ;  
  repeated Visit/type = TOEPh sub = Subject ;  
  lsmeans Treatment*Visit/pdiff cl alpha = 0.05 ;  
  run;
```

Based on the OC and LOCF data sets, analysis of covariance (ANCOVA) model with treatment (0.3% or 1% OPA-15406 group, and vehicle group) as a factor and baseline IGA as a covariate will be applied to the change from baseline up to each timepoint. The least square mean of each treatment group will be calculated by timepoint. The difference in the least square mean between the vehicle group and each OPA-15406 group, and the two-sided 95% confidence interval and p-value will also be calculated at Week 1, Week 4, and Week 8 (as well as at Week 2 and Week 6). Based on the OC and LOCF data sets, measured values and changes from baseline in IGA at Week 1, Week 4, and Week 8 (as well as at Week 2 and Week 6) will be summarized by treatment group using descriptive statistics.

The mean with standard error of measured values (in the OC and LOCF data sets) will be plotted by timepoint for each group.

Shift tables will be created for the change from baseline in IGA (-3, -2, -1, ±0, +1, +2) at Week 1, Week 4, and Week 8.

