6.4 Method of Minimizing or Avoiding Bias

This trial is a randomized, double-blind trial.

The IMP allocation manager will prepare a master “random allocation table” (hereinafter, “randomization table”) and conduct IMP coding according to the operating procedures for randomization. Also, the IMP allocation manager will prepare an emergency code list for use in emergencies such as the occurrence of a serious adverse event.

The investigator, subinvestigator, and subjects are blind to the IMP randomization code. Except for some designated personnel, the sponsor’s trial staff, including the personnel of contract research organizations, are also unable to access the IMP randomization code during the trial period.

Prior to the trial start and unblinding, the IMP allocation manager will confirm that the IMPs are indistinguishable. The randomization table is sealed by the IMP allocation manager just after completion of IMP randomization and it is kept under strict control until unblinding after fixation of all CRFs and the database.

The emergency code list will be kept under strict control by the registration system until the end of the trial. If a medical emergency occurs in a subject and knowledge of his or her IMP randomization code is considered important for treatment, the emergency code will be broken according to the “[8.2.4 Emergency Code Breaking \(Procedure for Unblinding During the Trial Period\)](#).”

When IMPs are recovered by the sponsor prior to unblinding, they are to be recovered sealed by the IMP allocation manager.

The subjects will be allocated to the 0.3% OPA-15406 group, the 1% OPA-15406 group, and the vehicle group in a ratio of 1:1:1 using dynamic allocation to ensure

balance within the trial sites and that of the baseline IGA (mild or moderate at the baseline examination).

The results of drug concentration measurements will not be revealed until unblinding at the end of the trial.

7 Observations/Examinations/Variables, Methods and Implementation Timings

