### 1) Screening period

After obtaining informed consent, the investigator or subinvestigator will perform a screening examination. The screening period is defined as the period between the day of the screening examination and the day of the baseline examination (2-30 days).

The subjects who meet the inclusion criteria and do not meet the exclusion criteria at the baseline examination will be dynamically allocated to the test product (0.3% or 1% formulation of OPA-15406) or the comparator (vehicle of OPA-15406), using the trial site and IGA at the baseline examination as the allocation factors.

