### **9.2.3 Changes From Baseline in Overall EASI Score and EASI Symptom Scores at Week 1, Week 4, and Week 8**

Based on the OC data set, the change from baseline in EASI score (at Week 1, Week 2, Week 4, Week 6, and Week 8; If the timing of discontinuation falls within the allowable window of a timepoint, the data at discontinuation will be included as the data for the timepoint) will be analyzed using the MMRM analysis with treatment (0.3% or 1% OPA-15406 group, and vehicle group), timepoint, and interaction between treatment and

timepoint as factors and baseline EASI score as a covariate. An unstructured covariance matrix will be used to model the within-subject errors and Kenward-Roger method will be used to calculate the standard error of fixed-effects and the degree of freedom. If the MMRM procedure fails to converge under unstructured covariance structure, the following structure will be used in the order of 1) heterogeneous toeplitz, 2) heterogeneous autoregressive of order 1, 3) heterogeneous compound symmetry, and the first (co)variance structure converging to the best fit will be used.

The least square mean of each treatment group will be calculated by timepoint. For overall EASI score, the least square mean and the standard error will be plotted by timepoint for each treatment group. The difference in the least square mean between the vehicle group and each OPA-15406 group, and the two-sided 95% confidence interval and p-value will be calculated at Week 1, Week 4, and Week 8 (as well as at Week 2 and Week 6). Based on the OC and LOCF data sets, ANCOVA model with treatment (0.3% or 1% OPA-15406 group, and vehicle group) as a factor and baseline EASI score as a covariate will be applied to the change from baseline up to each timepoint. The least square mean in each treatment group will be calculated by timepoint. The difference in the least square mean between the vehicle group and each OPA-15406 group, and the two-sided 95% confidence interval and p-value will be calculated at Week 1, Week 4, and Week 8 (as well as at Week 2 and Week 6). Based on the OC and LOCF data sets, measured values and changes from baseline in IGA at Week 1, Week 4, and Week 8 (as well as at Week 2 and Week 6) will be summarized by treatment group using descriptive statistics. For the overall EASI score, the mean with standard error of measured values (in the OC and LOCF data sets) will be plotted by timepoint for each treatment group.

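### Trial site is an allocation factor but is absent from the MMRM and ANCOVA models for the continuous secondary endpoints, so their standard errors may be modestly too wide

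*SAP*

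**What the plan says.** SAP section 3 (Screening period) allocates subjects dynamically, "using the trial site and IGA at the baseline examination as the allocation factors". Protocol 6.4 says the same: three groups "in a ratio of 1:1:1 using dynamic allocation to ensure" balance within sites and on baseline IGA.

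The analysis models in SAP 9.2.2 and 9.2.3 are:

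- **IGA change, MMRM.** The terms are treatment, "timepoint, and interaction between treatment and timepoint as factors and baseline IGA as a covariate". The code agrees: the class line is "class Treatment Visit Subject" and the model line is "model Change = Treatment Visit Treatment*Visit Baseline/s ddfm = kr".
- **IGA change, ANCOVA.** An "analysis of covariance (ANCOVA) model with treatment (0.3% or 1% OPA-15406 group, and vehicle group) as a factor and baseline IGA as a covariate".
- **EASI.** The same two models, with treatment, timepoint and treatment by "timepoint as factors and baseline EASI score as a covariate".

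SAP 9.2.4 to 9.2.9 reuse the EASI models for VAS, VRS, DLQI, POEM, affected BSA and the percent changes. Site appears in none of them. For every continuous endpoint other than IGA change, baseline IGA is replaced by the endpoint's own baseline, so neither allocation factor is in the model.

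The SAP gives no reason for omitting site. Its remark in 13.1 about many sites with few subjects explains only why the by-site frequency table was dropped. SAP 6.6.1 gives the p-values of all non-primary variables as reference, without multiplicity adjustment.

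**The concern.** Balancing the arms within sites removes differences between sites from the treatment contrast. A model without site still counts those differences as residual error. The model-based standard error then describes more variation than the treatment estimate has: intervals are too wide, and tests reject less often than their nominal level.

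A site effect is plausible for IGA, EASI and affected BSA because the site's own investigator or subinvestigator scores them (Protocol 7.2.1.1, 7.2.1.2 and 7.2.1.7). At stake is precision that the allocation has already secured but the planned analysis would not report.

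**Working it through.** **Inputs.** From the documents: 180 subjects, 60 per arm, 1:1:1, allocation on site and baseline IGA, two-sided 5%. Assumed, because the documents under review do not give them: number of sites (10 to 45), site ICC after baseline adjustment (0 to 0.20), and how strictly the allocation forces balance.

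**The plan's own figure.** The plan states no standard error or power for these models. Its one design calculation, 54 per group for 20.93% against 2.70%, is reproduced by the exact power of Fisher's test (79.1% at 53, 80.2% at 54). It concerns the primary endpoint and does not bear on this point.

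**Step 1: formula.** Let the residual SD be 1. Without site, the reported SE of a two-arm difference is √(2/60) = 0.183. With exact balance within sites, the true SE is 0.183 × √(1 − ICC). The ratio of reported to true SE is k = 1/√(1 − ICC), and the actual size of the test is 2[1 − Φ(1.96k)].

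| Residual ICC | k | Actual size |
|---|---|---|
| 0.02 | 1.010 | 4.8% |
| 0.05 | 1.026 | 4.4% |
| 0.10 | 1.054 | 3.9% |
| 0.20 | 1.118 | 2.8% |

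This is the upper limit, because real allocation does not balance every site exactly.

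**Step 2: simulated allocation.** Single-visit ANCOVA, with minimisation on site and IGA that always picks the best arm, 1,500 to 2,000 trials per setting, and 10, 20 and 45 sites:

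- ICC 0: ratio 1.00 (10 and 20 sites).
- ICC 0.05: ratio 1.02; size 4.7% to 5.0%.
- ICC 0.10: ratio 1.04 to 1.06; size 3.7% to 3.9%.
- ICC 0.20: ratio 1.09 to 1.10; size 3.0% to 3.5%.
- Simple randomisation, 20 sites, ICC 0.10: ratio 0.99. The excess therefore comes from balancing on site and then ignoring it.
- Looser rule (best arm with probability 0.80), ICC 0.10: ratio 1.02 (20 sites) and 1.03 (45 sites); size 5.1% and 4.7%, with Monte Carlo error of about 0.6 percentage points.

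**Step 3: gain from a random site term.** Best arm with probability 0.85, 20 or 40 sites, about 12,400 trials per setting, site variance treated as known:

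| ICC | SE falls by | Size without site | Power for 0.5 SD, without → with site |
|---|---|---|---|
| 0.05 | 2% | 4.7% | 78% → 79–80% |
| 0.10 | 4% | 4.0–4.2% | 78–79% → 81–82% |
| 0.20 | 8–9% | 3.4–3.8% | 79–80% → 85–86% |

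With the site variance estimated by REML (2,500 trials per setting), the SE falls by 2%, 4% and 9–10% (the last for 20 sites only). At ICC 0.20 the size moves from 3.4–3.5% to 5.0–5.2%. At ICC 0 the SE changes by less than 1% and power does not change.

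**Step 4: fixed or random site.** With 45 small sites and ICC 0.05, fixed site effects raised the mean SE from 0.182 to 0.185. A random intercept is the suitable form.

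**Step 5: the primary test.** With rates of 3% and 20% and no site effect (600 trials per setting), CMH by IGA had power of 88–89%. CMH by site × IGA had 82.5% with 20 sites and 72% with 40.

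**The case against.** The strongest case against is that the size is unknown and may be very small.

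- **A stable rater offset partly cancels.** The endpoints are changes from baseline with baseline in the model, and the same dermatologist should rate a subject throughout. Suppose an additive rater effect with raw-score ICC c and within-site baseline/follow-up correlation r. The baseline slope is b = c + r(1 − c). The residual site variance is c(1 − b)², against a within-site variance of (1 − c)(1 + b² − 2br). With c = 0.10 and r = 0.5, b = 0.55, and the residual ICC is 0.0203/(0.0203 + 0.677) = 0.03. For c = 0.05, 0.10 and 0.20 the residual ICC is 0.016, 0.03 and 0.05 at r = 0.5, and 0.025, 0.046 and 0.078 at r = 0.3. This stands, though r is assumed and the cancellation is less clean for IGA, where entry is limited to scores 2 and 3. The ICCs in the working must be read as values after baseline adjustment.
- **The rater argument does not reach every endpoint.** Subjects themselves score VAS, VRS, DLQI and POEM (Protocol 7.2.1.3 to 7.2.1.6). This stands. Sites may still differ on these, but the documents give no particular reason to expect it.
- **Rater and site need not coincide,** because a site may have several subinvestigators. This also stands.
- **The remedy is less simple than one added statement.** The estimated site variance was zero in about 19–25% of simulated trials at ICC 0.05 and about 40% at 0.02. The MMRM itself was not simulated, and its fallback code needs rewriting. This affects how the change is specified but does not remove the reason for it.
- **The CMH comparison assumed no site effect,** so it does not show how site stratification performs when sites differ. It supports leaving the primary test alone, but no more than that.

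**Conclusion.** The mismatch between allocation and analysis is plain in the documents and unexplained. Its consequence is conditional. If sites differ in baseline-adjusted change and allocation balances sites closely, the standard errors and intervals of the continuous secondary endpoints are about 2%, 4% and 9% too wide at residual ICCs of 0.05, 0.10 and 0.20. A nominal 5% test then runs at about 4.7%, 4% and 3.5%. With a looser allocation rule the excess at ICC 0.10 is 2–3%, with size close to nominal. The argument carries over to each visit's contrast in the MMRM, but the figures come from single-visit models.

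Two stronger readings are tempting. A reader might infer that the standard errors are materially too conservative for every listed endpoint whenever sites differ. The documents do not support that: they give no ICC, site count or allocation probability, and rater severity bears only on IGA, EASI and affected BSA. A reader might also infer a flaw in the trial's main conclusion. That does not follow either: the effect is conservative, the treatment estimate is unbiased, and the p-values concerned are for reference only. This is a precision improvement at little cost and does not correct an error in a confirmatory result.

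**What to change.** Before database lock, amend SAP 9.2.2 to 9.2.9 as follows:

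1. Add trial site as a random intercept to each ANCOVA and MMRM, with subjects nested in site. For the MMRM, state whether the site effect is taken as constant across visits.
2. State that the term is dropped if its variance is estimated as zero, and that this may be common if the ICC is low.
3. Restate the MMRM fallback code. It now uses the `empirical` option with Subject as the cluster; the option and the clustering must be made consistent with the site term.
4. Leave the primary CMH test stratified by baseline IGA only.

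If the sponsor prefers to keep the models as they are, one sentence should say why an allocation factor is omitted.

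The cost is a few lines of SAP text and code, and a check that the models converge. No additional data or subjects are needed, and if sites do not differ the simulated loss of precision is under 1%.

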### **9.2.3 Changes From Baseline in Overall EASI Score and EASI Symptom Scores at Week 1, Week 4, and Week 8**

Based on the OC data set, the change from baseline in EASI score (at Week 1, Week 2, Week 4, Week 6, and Week 8; If the timing of discontinuation falls within the allowable window of a timepoint, the data at discontinuation will be included as the data for the timepoint) will be analyzed using the MMRM analysis with treatment (0.3% or 1% OPA-15406 group, and vehicle group), timepoint, and interaction between treatment and

timepoint as factors and baseline EASI score as a covariate. An unstructured covariance matrix will be used to model the within-subject errors and Kenward-Roger method will be used to calculate the standard error of fixed-effects and the degree of freedom. If the MMRM procedure fails to converge under unstructured covariance structure, the following structure will be used in the order of 1) heterogeneous toeplitz, 2) heterogeneous autoregressive of order 1, 3) heterogeneous compound symmetry, and the first (co)variance structure converging to the best fit will be used.

The least square mean of each treatment group will be calculated by timepoint. For overall EASI score, the least square mean and the standard error will be plotted by timepoint for each treatment group. The difference in the least square mean between the vehicle group and each OPA-15406 group, and the two-sided 95% confidence interval and p-value will be calculated at Week 1, Week 4, and Week 8 (as well as at Week 2 and Week 6). Based on the OC and LOCF data sets, ANCOVA model with treatment (0.3% or 1% OPA-15406 group, and vehicle group) as a factor and baseline EASI score as a covariate will be applied to the change from baseline up to each timepoint. The least square mean in each treatment group will be calculated by timepoint. The difference in the least square mean between the vehicle group and each OPA-15406 group, and the two-sided 95% confidence interval and p-value will be calculated at Week 1, Week 4, and Week 8 (as well as at Week 2 and Week 6). Based on the OC and LOCF data sets, measured values and changes from baseline in IGA at Week 1, Week 4, and Week 8 (as well as at Week 2 and Week 6) will be summarized by treatment group using descriptive statistics. For the overall EASI score, the mean with standard error of measured values (in the OC and LOCF data sets) will be plotted by timepoint for each treatment group.

EASI scores for body regions (face, neck, and head, upper limbs, trunk, and lower limbs) will be analyzed in the same manner as the overall EASI score.

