A mixed-model repeated measure (MMRM) analysis with an unstructured error covariance matrix will be performed, using the OC data set containing the data at baseline, after administration (Week 1, Week 2, Week 4, Week 6, and Week 8), and at discontinuation, setting the change from the baseline at Week 1 through Week 8 as a response variable and the treatment (0.3% OPA-15406, 1% OPA-15406, or vehicle), timepoint, baseline IGA (mild or moderate), interaction between the treatment (0.3% OPA-15406, 1% OPA-15406, or vehicle) and timepoint as factors. Standard error and degree of freedom for the fixed effect will be calculated by the Kenward-Roger method. The least square mean will be calculated by treatment group and timepoint. Also, the difference in the least square means between the vehicle group and the respective OPA-15406 groups, the two-sided 95% confidence interval, and the p value will be calculated at Week 1, Week 4 and Week 8. Using the OC and LOCF data sets, the analysis of covariance (ANCOVA) with treatment (0.3% OPA-15406, 1% OPA-15406, or vehicle) and baseline IGA (mild or moderate) as factors will be applied to the change from the baseline at the respective timepoints as a response variable. The least square mean will be calculated by treatment group and timepoint. Also, the difference in the least square means between the vehicle group and the respective OPA-15406 groups, the two-sided 95% confidence interval, and the p value will be calculated at Week 1, Week 4 and Week 8. Using the OC and LOCF data sets, the descriptive statistics will be calculated for measured values and changes from

the baseline at the respective timepoints by treatment group and timepoint. For the change in IGA at Week 1, Week 4, and Week 8, the frequency distribution will also be generated.

- For the following items, the analysis will be performed in the same manner as that of the change from baseline at the respective timepoints in IGA. For the MMRM analysis, however, the treatment (0.3% OPA-15406, 1% OPA-15406, or vehicle), timepoint, and interaction between the treatment and timepoint will be used as factors, and baseline values of the respective variables will be used as covariates. For the ANCOVA model, baseline values of the respective variables will also be included as covariates, as well as the treatment. For EASI, VAS, and DLQI, the percent change from baseline at the respective timepoints will also be calculated in the same manner as the amount of change.

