#### **9.2.4 Change From Baseline in Visual Analogue Scale for Pruritus at Week 1, Week 4, and Week 8**

The change from baseline in visual analogue scale (VAS) for pruritus will be analyzed in the same manner as that in the overall EASI score or each EASI symptom score.

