#### **9.2.5 Change From Baseline in VRS for Pruritus up to Day 7**

The change from baseline in VRS for pruritus up to Day 7 will be analyzed in the same manner as that in overall EASI score or each EASI symptom score. Data will be collected

at baseline, 4, 8, and 12 hours after the start of administration, 1 day after the start of administration (morning and night), and thereafter in the same manner up to Day 7 (morning). The same analysis will be performed by the time zone of assessment (morning or evening). Morning or evening will be determined based on the time label entered in the case report form (CRF), not using the timepoints defined in Table 6.4-2, except the baseline, which is irrespective of the time zone of assessment. Data will be collected at baseline, and the timepoints specified above on Day 1 to Day 7.

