#### **9.2.6      Change From Baseline in Dermatology Life Quality Index Score at Week 1, Week 4, and Week 8**

The change from baseline in Dermatology Life Quality Index (DLQI) score will be analyzed in the same manner as that in the overall EASI score or each EASI symptom score. The DLQI scores will be classified into the following categories and a shift table at baseline, Week 1, Week 4, and Week 8 will be created.

DLQI score categories: 0 to 1, 2 to 5, 6 to 10, 11 to 20, and 21 to 30

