#### **9.2.8      Change From Baseline in Overall Percentage Affected BSA at Week 1, Week 4, and Week 8**

The change from baseline in overall percentage affected BSA will be analyzed in the same manner as that in the overall EASI score or each EASI symptom score.

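### The EASI, VAS, VRS, DLQI, POEM and affected-BSA models omit baseline IGA, an allocation factor, so their reported standard errors may be somewhat too large

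*SAP*

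**What the plan says.** SAP section 3 (Screening period) describes dynamic allocation "using the trial site and IGA at the baseline examination as the allocation factors". Protocol 6.4 gives the ratio as 1:1:1, and the entry criteria restrict baseline IGA to 2 (mild) or 3 (moderate).

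The primary Cochran-Mantel-Haenszel test is stratified by baseline IGA (SAP 9.1 and 9.4).

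The other continuous efficacy models are built differently:
- **EASI, MMRM (SAP 9.2.3):** treatment, "timepoint as factors and baseline EASI score as a covariate".
- **EASI, ANCOVA (SAP 9.2.3):** treatment "as a factor and baseline EASI score as a covariate will be applied to the change from baseline up to each timepoint".
- **VAS (SAP 9.2.4):** "will be analyzed in the same manner as that in the overall EASI score or each EASI symptom score".
- **VRS (SAP 9.2.5):** "The change from baseline in VRS for pruritus up to Day 7 will be analyzed in the same manner as that in overall EASI score".
- **DLQI, POEM and affected BSA (SAP 9.2.6 to 9.2.8):** the same cross-reference to EASI.
- **Percent changes (SAP 9.2.9):** the same models again, for EASI, VAS, DLQI and POEM.

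Protocol 11.3.1.2 sets the rule that the SAP follows: for the MMRM of EASI, VAS, DLQI, POEM and affected BSA, "baseline values of the respective variables will be used as covariates". Its VRS ANCOVA also uses treatment and own baseline only. Neither document says why baseline IGA is left out, and trial site is in none of the efficacy models.

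**The concern.** When allocation forces the arms to be alike on a prognostic factor, chance imbalance in that factor no longer contributes to the error of the treatment difference. A model without the factor still counts its variance as residual noise. The standard error it reports is then larger than the error the design actually produces, so confidence intervals are too wide and tests reject too rarely under the null.

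These models supply the intervals and p-values for every continuous secondary efficacy endpoint other than change in IGA, in a dose-finding trial. Any overstatement would blur comparisons of each concentration with vehicle, although it would not favour the drug.

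**Working it through.** **The plan's own figure.** The documents state no standard error, SD or power for these endpoints. The only related figure is 54 per group for the primary endpoint (20.93% against 2.70%, two-sided 5%, at least 80% power). Fisher's exact test reproduces it: power is 79.1% at 53 per group and 80.2% at 54. Then 54/0.9 = 60. Nothing below touches this calculation.

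**Inputs.**
- From the documents: three arms of 60, 180 subjects in total; binary baseline IGA; own baseline already in every model.
- Assumed, because the documents are silent: partial R² of baseline IGA given own baseline of 0, 0.02, 0.05 or 0.10; 35% of subjects mild; correlation ρ = 0.5 between IGA and own baseline; exact balance on IGA; a single-visit ANCOVA.

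**Step 1: reported standard error.** Leaving IGA out multiplies the residual variance by 1/(1 − R²), so

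model SE ratio (without IGA / with IGA) = 1/√(1 − R²).

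- R² = 0: 1.000
- R² = 0.02: 1/√0.98 = 1.010
- R² = 0.05: 1/√0.95 = 1.026
- R² = 0.10: 1/√0.90 = 1.054

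Simulation under these assumptions gives the same ratios. A separate simulation with a 50:50 mild/moderate split gave 1.02 at partial correlation 0.2 (R² = 0.04) and 1.05 at 0.3 (R² = 0.09). The formula gives 1.021 and 1.048, so the result does not hinge on the mild/moderate split.

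**Step 2: true sampling error.** With exact balance, omitting IGA adds no direct imbalance term. It only shifts the slope on own baseline, because that slope absorbs part of the IGA effect. Writing k = R²/(1 − R²),

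true SD ratio (without IGA / with IGA) ≈ √(1 + ρ²k).

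- R² = 0.02: k = 0.0204, √(1 + 0.25 × 0.0204) = 1.003
- R² = 0.05: k = 0.0526, √(1 + 0.25 × 0.0526) = 1.007
- R² = 0.10: k = 0.1111, √(1 + 0.25 × 0.1111) = 1.014

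Simulated values agree within Monte Carlo error, at about 0.1–0.2%, 0.5–0.7% and 1.2–1.4%.

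**Step 3: test size.** Simulated rejection at a nominal 5% with IGA omitted is about 4.0% at R² = 0.10. It is about 5% when the partial correlation is 0 or 0.1. With IGA included it stays close to 5%.

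**Step 4: on a subject scale.** In reported interval width, 180 × (1 − R²) = 176.4, 171 and 162, a shortfall of about 4, 9 and 18 subjects. In true information, 180/(1 + ρ²k) = 179.1, 177.7 and 175.1, a shortfall of about 1, 2 and 5.

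**The case against.** The strongest case against is that this is a preference about efficiency and not an error. Own-baseline ANCOVA and MMRM are prespecified in the protocol, and the SAP follows them. The change-in-IGA models do carry baseline IGA, but there it is the variable's own baseline, so the SAP applies one rule to all continuous endpoints and is not at odds with itself. The only real contrast is with the primary test. IGA and EASI both grade erythema and infiltration/papules (Protocol 7.2.1.1 and 7.2.1.2), so baseline EASI may already hold most of what IGA would add. Any error is conservative and falls on endpoints that Protocol 11.3.7 and SAP 6.6.1 treat as reference only.

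Most of this stands, and it limits the size of the point. The overlap argument is weaker for the other scores: the rationale in Protocol 3.3 says IGA leaves out subjective symptoms and affected BSA, so pruritus, DLQI, POEM and BSA baselines are different constructs. Whether IGA adds prediction there is unquantified, but it cannot be assumed to be nil.

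Two stronger readings are tempting. A reader might infer that the standard errors are definitely inflated for all six scores; the documents give no partial correlation, and at zero there is no inflation. A reader might also infer that omitting IGA amounts to discarding up to 18 of 180 subjects. That figure describes reported interval width; the information actually lost is about 5 subjects or fewer under the same assumptions.

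Site is an allocation factor too. SAP 13.1 mentions many sites and few subjects per group, but gives that as the reason for dropping a descriptive table, not for leaving site out of the models.

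**Conclusion.** The point holds as a minor improvement. Baseline IGA is an allocation factor and is missing from the EASI, VAS, VRS, DLQI, POEM and affected-BSA models. So far as it predicts change beyond own baseline, reported standard errors are too large: by about 1.0%, 2.6% and 5.4% at assumed partial R² of 0.02, 0.05 and 0.10, and not at all at 0. True sampling error changes by only about 1% (0.3% to 1.4% over that range).

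These sizes rest on the assumptions listed in the working. The multi-visit MMRM and the balance that dynamic allocation actually achieves would shift them slightly. The direction is conservative, the endpoints are secondary, and the primary analysis and the sample size are not affected.

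**What to change.** Add baseline IGA (mild or moderate) as a class factor to the MMRM and ANCOVA models in SAP 9.2.3 to 9.2.9, keeping each score's own baseline. Do this before database lock, and record the change and its reason in SAP 13.1; Protocol 11.4 requires this, and an account in the clinical study report, when a protocol-specified method is changed. If the sponsor prefers to keep the present models, state why baseline IGA is left out.

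Site may stay out because subjects per site are few, but the SAP should give that as the reason for the models themselves.

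The cost is one model term, one degree of freedom out of roughly 175, and a short entry in the change record. No new data are needed.
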